9.5.7. Prior and Concomitant Therapy

All treatments being taken by the patients on entry to the study or at any time during the study in addition to the investigational product are regarded as concomitant treatments and must be documented on the appropriate section of the eCRF. A history of all prior medications needs to be documented to at least 4 weeks prior to study participation, and a history of previous treatments for MS needs to be documented for at least the prior 2 years.

Concomitant treatment with any of the medications listed below is not allowed during the study or some time prior to randomization.

Medications that must be discontinued prior to randomization and cannot be used during the study:

- Non-lymphocyte-depleting disease-modifying MS agents (e.g., glatiramer acetate, interferons) must be discontinued from signing of informed consent until randomization for a minimum of 2 weeks;

- Treatment with medications with a known impact on the cardiac conduction system (e.g., beta blockers, calcium channel blockers, Class Ia or Class III anti-arrhythmics). A list with examples of prohibited cardiac medications is provided in [Table 8](#) (note that this is not a comprehensive list and other drugs in these classes are also excluded. Refer to the Study Reference Manual and contact the Medical Monitor for further guidance if needed).

Medications that must be discontinued at least 4 weeks prior to randomization and cannot be used during the study:

- Systemic corticosteroid therapy or ACTH is not allowed within 30 days prior to screening, except for treatment of protocol-defined treatment of relapses ([Section 9.1.2.3](#)). Corticosteroids that are by non-systemic routes (e.g., topical, inhaled, intraarticular) are allowed.
- Inducers or inhibitors of CYP3A4 metabolism. A list with examples of medications that may affect the metabolism of RPC1063 is provided in [Table 9](#) (note that this is not a comprehensive list and other drugs in these classes are also excluded. The Medical Monitor should be contacted for further guidance as needed).
- Live vaccines.

Medications that must be discontinued 3 months prior to randomization and cannot be used during the study:

- Treatment with IVIg or plasmapheresis
- Treatment with other disease modifying therapies (e.g., daclizumab, dimethyl fumarate, laquinimod)
- Teriflunomide. Treatment with teriflunomide is not permitted within 3 months prior to randomization. In addition, if a patient has received teriflunomide treatment within 6 months of randomization either of the two following accelerated elimination procedures must be followed, according to the manufacturer's protocol ([Genzyme, 2012](#)).
 - Administration of cholestyramine 8 g every 8 hours for 11 days. If cholestyramine 8 g three times a day is not well tolerated, cholestyramine 4 g three times a day can be used.
 - Administration of 50 g oral activated charcoal powder every 12 hours for 11 days.

If either elimination procedure is poorly tolerated, treatment days do not need to be consecutive.

Medications that must be discontinued 6 months prior to randomization and cannot be used during the study:

- Immunosuppressive agents (e.g., azathioprine, cyclosporine, methotrexate, or mycophenolate)
- Any other investigational agent

Medications that cannot be used at any time prior to randomization (i.e. are exclusionary and any prior use is prohibited):

- Lymphocyte-trafficking inhibitors (fingolimod, natalizumab)
- Immunosuppressive agents that deplete lymphocytes (e.g., alemtuzumab, anti-CD4, cladribine, rituximab, ocrelizumab, cyclophosphamide, mitoxantrone)

Table 8 Examples of Prohibited Cardiac Medications

Pharmaceutical Class	Example Medications
Beta blockers	acebutolol, atenolol, betaxolol, bisoprolol, metoprolol, nadolol, propranolol, sotalol, timolol
Calcium channel blockers	diltiazem, verapamil
Anti-arrhythmic drugs	amiodarone, bepridil hydrochloride, disopyramide, dofetilide, dronedarone, flecainide, ibutilide, lidocaine, procainamide, propafenone, quinidine, tocainide
QT prolonging drugs	Citalopram (>20 mg/day), chlorpromazine, haloperidol, methadone, erythromycin

Table 9 Examples of Prohibited Inducers or Inhibitors of CYP3A4

Pharmaceutical Class	Example Medications
HIV protease inhibitors	indinavir, nelfinavir, ritonavir, atazanavir, saquinavir
Antibiotics	clarithromycin, telithromycin, rifampin, rifamycin
Antifungals	itraconazole, ketoconazole, fluconazole
Anticonvulsants	phenobarbital, phenytoin, carbamazepine
Others medications	nefazodone, pioglitazone, troglitazone, amiodarone, cyclosporine
Foods and herbal supplements	grapefruit juice, Seville orange juice, St. John's Wort

Treatment for symptoms related to MS (e.g., spasticity, incontinence, pain, fatigue, and depression) is not restricted but investigators should attempt to keep therapies or treatments reasonably constant throughout the study. Patients should have been on a stable dose for 3 months prior to screening. Changes may be made if appropriate for a patient's well-being in the clinical judgment of the treating investigator.

Administration of concomitant medications must be reported in the appropriate section of the eCRF along with dosage information, dates of administration, and reasons for use. For medications with a single active ingredient, generic names for concomitant medication should be used, if possible. For combination products, brand names should be used. The total daily dose should be filled in whenever possible.

9.5.8. Concomitant Procedures

Immunosuppressive procedures that deplete lymphocytes (e.g., total body irradiation, bone marrow transplantation) are not allowed during the study or at any time prior to the study.

Concomitant procedures must be reported in the appropriate section of the eCRF. AEs related to these therapies or procedures must be documented on the patient's eCRF.

9.5.9. Treatment Compliance

It is the Investigator's responsibility to ensure that patients are correctly instructed on how to take their study medication and that each patient is fully compliant with their assigned dosage regimen. Records of study medication used and intervals between visits will be kept during the study. Drug accountability will be noted by the field monitor during site visits and at the completion of the study. Patients will be asked to return all unused medication at the end of the study. The study treatment should be dispensed by the Investigator, or by a qualified individual under the Investigator's supervision. An up-to-date treatment inventory/dispensing record must be maintained as described above in [Section 9.5.5.2](#).

Overall study non-compliance is defined as taking less than 80% or more than 120% of study medication during the entire treatment period.

Details unique to Parts A or B are described below.

Part A

At each visit, previously dispensed study medication capsules will be collected by the Investigator and compliance assessed. Patients will record capsules intake in a dosing diary that will be reviewed periodically by site staff and the Clinical Monitor. Patients exhibiting poor compliance as assessed by medication counts (i.e., 2 or more missed medication days in 1 week) and response to the question "Did you take your medication regularly?" should be counseled on the importance of good compliance to the study dosing regimen. Patients who are persistently non-compliant (< 80% or > 120%) should be discussed with the Medical Monitor to determine whether they should be withdrawn from the study.

Part B

Compliance with IFN β -1a dosing is to be monitored and recorded by site staff. Patients will record IFN β -1a treatment in a dosing diary that will be reviewed periodically by site staff and the Clinical Monitor.

Compliance with RPC1063 capsules will be assessed as described above for Part A.

9.5.10. Assignment to Treatment

Patients must provide proper informed consent before any study procedures are performed (refer to [Section 5.3](#) for further details regarding obtaining patients informed consent). At the time of consent the patient is enrolled in the study. In Parts A and B patients will be randomized into the study on Day 1 after all screening and baseline assessments have been completed and the Investigator has verified that the patient is eligible per the inclusion ([Section 9.4.1](#)) and exclusion criteria ([Section 9.4.2](#)).

Randomization will be performed through an IVRS (Section 13.4). Treatment groups are described in Section 9.5.1. Details unique to Parts A or B are described below.

Part A

Patients will be stratified by country and will be randomized 1:1:1 to receive placebo, 0.5 mg RPC1063, or 1 mg RPC1063.

Part B

Patients will be stratified by baseline EDSS (≤ 3.5 , > 3.5) and country and will be randomized 1:1:1 to receive IFN β -1a 30 μ g, or 0.5 mg RPC1063, or 1 mg RPC1063.

9.5.11. Unblinding Procedures for Individual Patients

A patient's treatment group assignment blind will not be broken until the end of the study unless medical treatment of that patient depends upon knowing whether the patient is receiving active drug. In the event that the blind needs to be broken because of a medical emergency, the investigator may unblind an individual patient's treatment allocation. The investigator should attempt to contact the Medical Monitor as soon as practicable to discuss the medical emergency and the reason unblinding. The treatment assignment will be unblinded through an IVRS. Reasons for treatment unblinding must be clearly explained and justified in the eCRF. The date on which the code was broken together with the identity of the person responsible must also be documented.

A PK sample will be obtained whenever possible for patients with any AE resulting in unblinding, discontinuation or SAE.

10. STUDY SCHEDULE

The study design is shown in . Tests and Assessments are outlined in [Table 1](#) and [Table 2](#) (Part A), [Table 3](#) and [Table 4](#) (Part B), and [Table 5](#) (cardiac monitoring during dose titration). Methods of assessment are described in [Section 11](#).

It is recommended that the study visits are scheduled in the morning. At the Baseline visit, and on days of study visits on which a predose PK sample is to be obtained (Part A Week 12 and Part B Month 12), patients should be instructed to withhold the dose and the morning meal until the office visit, and dose will be administered during the visit.

Whenever possible, the sequence of when the efficacy assessments are done (EDSS, MSFC) should remain constant and at approximately the same time of day throughout the study. Assessment of the MSFC should start with walking, and it should be done before walking for EDSS.

Predose blood samples for PK evaluation are to be taken 5 to 30 minutes prior to study treatment administration. Actual sampling times must be accurately recorded in the source document and appropriate eCRF. On days of study visits with collection of predose PK blood samples, patients must arrive at the site in fasting conditions.

On days of study visits on which a postdose PK sample is to be obtained, patient visits should be scheduled so a sample can be obtained 2 to 6 hours after the patient's usual dosing time. The patient should also be instructed to ensure that the dosing time is accurately recorded in the dosing diary.

It is recommended that procedures are performed in the following order (note that not all procedures are performed at every visit):

- Spontaneous or solicited AE reporting
- ECG
- Vital signs
- Clinical laboratory tests, including predose PK sampling
- Physical examination
- Efficacy assessments.

Specified visit windows (other than visits during dose titration) may be extended on a case by case basis if needed to accommodate scheduling *except* for the following procedures:

- Brain MRI
- EDSS and neurological examination

10.1. Screening Period (Part A and Part B)

Every effort should be made to complete all screening procedures within 30 days prior to receiving the first dose of study treatment in Part A or B of the study. If necessary, the Principal Investigator (or designee) may extend the Screening Period if needed to a maximum of 45 days

to accommodate scheduling of screening and baseline procedures. If screening procedures cannot be completed within 45 days, the Medical Monitor must be contacted for approval for any further extension, and to discuss whether any Screening procedures must be repeated prior to randomization. All screening assessments and procedures are to be performed by the Principal Investigator or a qualified designee.

Written, signed, and dated informed consent from the patient prior to the performance of any study-related procedures must be obtained by the Principal Investigator or designee (refer to [Section 5.3](#) for further details regarding obtaining patients informed consent). A copy of the signed informed consent must be given to the patient for his/her records.

Screening Period

During the screening period, the following procedures will be performed:

- Obtain patient's informed consent
- Inclusion/exclusion criteria
- Complete medical history
- Blood/urine sampling for the following laboratory tests:
 - Hematology: red blood cell (RBC) count, total and differential WBC count (basophils, eosinophils, lymphocytes, monocytes, and neutrophils), platelet count, hemoglobin, hematocrit, mean corpuscular volume (MCV), mean corpuscular hemoglobin (MCH), and mean corpuscular hemoglobin concentration (MCHC)
 - Blood chemistry: sodium, potassium, chloride, calcium, magnesium, phosphate, blood urea nitrogen, random glucose, albumin, alkaline phosphatase, creatinine, SGPT/ALT, SGOT/AST, gamma glutamyltransferase (GGT), amylase, total bilirubin, conjugated bilirubin, hemoglobin A1c. Abnormal laboratory parameters inconsistent with clinical presentation of MS or suspicious of underlying medical condition should be repeated for accuracy.
 - Urinalysis: leukocytes, specific gravity, bilirubin, blood, glucose, ketones, pH, protein, and urobilinogen
 - Serum beta-human chorionic gonadotrophin (β -hCG) (women of childbearing potential only)
 - Coagulation panel: prothrombin time (PT) and partial thromboplastin time (PTT)
 - Sensitive thyroid stimulating hormone (sTSH)
 - [REDACTED]
 - Viral serology: HIV antibodies, anti-hepatitis A virus IgM, HBsAg and HBcAg IgM, anti-HCV IgG or IgM. In addition, patients must have documentation of positive VZV IgG antibody status. Patients who are negative for VZV IgG antibodies at screening can undergo vaccination and be enrolled 30 days after appropriate VZV vaccination has been completed. Patients testing positive for HIV or for serological markers of acute or chronic hepatitis A, B, or C will be

excluded from the study unless they are indicative of prior hepatitis B vaccination or cured hepatitis A or B and accompanied by normal liver transaminase values.

- Syphilis RPR. Patients must have a negative result to be enrolled.
- TB testing. TB testing will include the purified protein derivative test. All testing must be completed prior to administration of study drug on Day 1. As available locally, an interferon gamma release assay such as QuantiFERON Gold test or other comparable interferon gamma release assay test (e.g., T-SPOT) may be used as an alternative TB screening test. Patients testing positive for TB with the purified protein derivative skin test or interferon gamma release assay will be excluded from the study unless there is (1) a history of either prior TB vaccination or well-documented cured TB/treatment of tuberculin conversion that is (2) accompanied by a chest x-ray negative for active infection, taking into account the subject's risk for TB based on history of contact, symptoms and physical signs. The investigator should consult an infectious disease physician if needed
- Complete physical examination: including evaluation of heart, lung, head and neck, abdominal, neurological, skin, and extremities. Note: Neurological evaluation should include fundoscopic examination to rule out uveitis and other clinically significant ophthalmologic abnormalities, which should be recorded in source documents.
- Height and weight
- Vital signs: body temperature, blood pressure and heart rate
- Chest X-ray: not required if performed within 60 days prior to randomization and if documentation is on file
- 12-lead ECG: the screening ECG report from the central reader must be available to confirm patient eligibility before randomization
- Enroll patient, contact IVRS
- EDSS and neurological examination
- Brain MRI
- MSFC practice. Three MSFC practice assessments must be performed before baseline: MSFC Practice 1 is to be performed at the screening visit, MSFC Practice 2 and MSFC Practice 3 may also be performed at the screening visit, or on other days between the screening and baseline visit).
- LCLA
- Pulmonary function tests including FEV₁ and FVC measurements, and DLCO
- OCT evaluation
- Dermatological examination.
- Suicidality assessment using the C-SSRS

- Record relevant prior and current therapy. A history of all prior medications needs to be documented to at least 4 weeks prior to study participation, and a history of previous treatments for MS needs to be documented for the prior 2 years
- SAEs to be recorded from the time of signing the informed consent; AEs to be recorded from the first dose of study drug.

10.1.1. Screen Failure

A screen failure is defined as a patient who has given informed consent, and failed to meet the inclusion and/or exclusion criteria.

10.1.2. Rescreening of Patients

Patients who fail to meet the inclusion/exclusion criteria can be rescreened. The Medical Monitor should be contacted prior to rescreening to discuss whether any prior screening results may still be used for rescreening.

10.2. Part A Treatment Period

10.2.1. Baseline/Day 1 Visit

Eligible patients will be randomized to treatment group on Day 1.

The following assessments will be performed at the baseline/Day 1 visit:

- Review of inclusion/exclusion criteria
- An interim medical history will be performed to complete the screening medical history. Medical events that occur between screening and first dose will be recorded as medical history.
- Blood/urine sampling for the following laboratory tests:
 - Hematology: RBC count, total and differential WBC count (basophils, eosinophils, lymphocytes, monocytes, and neutrophils), platelet count, hemoglobin, hematocrit, MCV, MCH, and MCHC
 - Blood chemistry: sodium, potassium, chloride, calcium, magnesium, phosphate, blood urea nitrogen, random glucose, albumin, alkaline phosphatase, creatinine, SGPT/ALT, SGOT/AST, GGT, amylase, total bilirubin, conjugated bilirubin.
 - Urine beta-hCG (females of childbearing potential only). If the urine pregnancy test is positive, do not dose and confirm with a serum pregnancy test.
 - Standard PK sampling: PK sample is to be taken prior to dose administration
 - [REDACTED]
 - [REDACTED]
- Weight

- Vital signs: body temperature, blood pressure and heart rate. See the special monitoring procedures below that will be performed on Day 1
- 12-lead ECG. See the special monitoring procedures below that will be performed on Day 1
- Continuous Holter monitoring (15 minutes predose and for 24 hours following dose). See the special monitoring procedures below that will be performed on Day 1
- Randomization
- Dispense study drug (with titration kit) and patient diary, and administer first dose of study drug at the site
- MSFC AND LCLA
- MSQOL-54
- Suicidality assessment using the C-SSRS
- Record concomitant therapy
- Record AEs/SAEs

10.2.1.1. Guidelines for Monitoring Patients Taking Their First Dose of RCP1063

On Day 1 of treatment, careful cardiac monitoring of the patients is required. The treating physician is responsible for monitoring the patient following the first intake of the study drug, as well as managing bradycardia symptoms should they occur. He or she must review the baseline predose ECG, vital signs during the 6-hour monitoring period, post-dose ECG, and assess discharge status at 6 hours after dosing. Baseline predose ECG should be provided by the site and be available for comparison to the postdose ECG in order to determine if criteria requiring extended monitoring are met. In addition, continuous Holter monitoring will be performed beginning 15 minutes predose and for 24 hours after dose administration. Further details on ECG and Holter monitoring procedures are provided in the Holter Manual.

Heart rate, blood pressure, and other vital signs will be measured before the first dose of study drug, then every hour for at least 6 hours thereafter (by the treating physician or an assisting nurse). Blood pressure and heart rate will be measured in the supine position and then the standing position at each time point. When obtaining the predose heart rate before the first dose, the patient should be allowed to rest in the supine position for 10 to 15 minutes before taking the heart rate. The supine heart rate and blood pressure measurements should be repeated 2 additional times to produce 3 readings for both heart rate and blood pressure (before the first dose of study drug only). The lowest predose value of supine heart rate and blood pressure (based on systolic blood pressure) will be recorded in the case report form and should be used for comparison to the postdose values. Orthostatic blood pressure will then be measured once with the patient in the standing position (after standing for 2 minutes) before the first dose of study drug.

Patients should receive the first dose of study drug in a fasted condition before 12:00 pm (noon) in the clinic. The first dose of RPC1063 should be administered in a setting in which resources to appropriately manage symptomatic bradycardia are available. A member of the Investigator team

should be available to monitor the patient for the 6 hours monitoring period and will need to report any abnormalities to the treating neurologist. Atropine needs to be readily available to the site personnel.

Additional extended monitoring should be instituted until the finding has resolved in the following situations:

- The heart rate 6 hours post-dose is < 45 bpm
- The heart rate 6 hours post-dose is at the lowest value post-dose (suggesting that the maximum PD effect on the heart may not have occurred)
- The ECG 6 hours post-dose shows new onset second degree or higher AV block
- The ECG 6 hours post-dose shows a prolonged QTcF interval (>450 msec males, >470 msec females).

Should post-dose symptomatic bradycardia occur, the treating neurologist should be notified and he or she should initiate appropriate management, begin continuous ECG monitoring, and continue observation until the symptoms have resolved.

Should a patient require pharmacologic intervention for symptomatic bradycardia, continuous overnight ECG monitoring in a medical facility should be instituted, and the first dose monitoring strategy should be repeated the following day (Day 2). The first dose monitoring strategy should also be repeated at Day 5 if any cardiac safety issues were observed on Day 1.

Patients should have written instruction on when to return to clinic and a 24-hour contact phone number to call in the event of any new or warranted symptoms (e.g., chest pain, dizziness, palpitations, syncope, nausea, vomiting). Patients should be instructed not to drive on the same day after the first dose of study drug administration.

First dose monitoring procedures will also be followed at the Week 24 visit in Part A for patients who elect to continue in the blinded extension study, or for any patient who resumes treatment after missing more than 7 consecutive doses.

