11.2. Safety Assessments

11.2.1. Clinical Safety Assessments

Physical Examination

A complete physical examination will include evaluation of heart, lung, head and neck, abdominal, skin, and extremities. The EDSS, performed by the blinded evaluator, serves as the neurological examination. An interim (or brief) physical examination will include areas with previously noted abnormalities and/or that are associated with any new complaints from the patient.

Initial neurological examination will be a part of the physical examination at screening and if warranted by an unscheduled visit. All significant findings that are present at screening must be reported on the relevant medical history/current medical conditions eCRF. Significant findings made after randomization that meet the definition of an AE must be recorded on the AEs eCRF.

Height and Weight

Height will be measured at screening in Part A and Part B and at the end of the study.

Weight will be measured at screening, Baseline (Day 1), Week 24 and end of study or early termination in Part A and screening, Baseline (Day 1), Month 12, and Month 24 or early termination in Part B.

Vital Signs

Blood pressure, heart rate and body temperature will be assessed.

For the Baseline (Day 1) visit and during dose titration (Day 5 and Day 8, as applicable), vital signs should be recorded after the patient has been supine for 10-15 minutes, systolic and diastolic blood pressure and heart rate will be measured 3 times using an automated validated device. The repeat measurements will be made at 2-minute intervals and the lowest of the 3 measurements will be recorded on the eCRF, based on systolic BP. For all other visits, vital signs will be assessed once and recorded on the eCRF.

In case the cuff sizes available are not large enough for the patient's arm circumference, a sphygmomanometer with an appropriately sized cuff may be used. Orthostatic blood pressure will then be measured once with the patient in the standing position (after standing for 2 minutes). A sudden, significant fall in blood pressure (>20 mmHg) between 2 and 5 minutes after standing from the supine position will be interpreted as an orthostatic hypotension and will be documented in the patient chart and eCRF.

Patients will be carefully monitored after the first dose of study medication with a 6 hour post-dose monitoring period of hourly recording of orthostatic blood pressure.

Chest X-ray

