## 10.3 Vital Sign Measurements

Vital signs including standing and supine systolic blood pressure (SBP), standing and supine diastolic blood pressure (DBP), body temperature, and heart rate (HR) will be recorded on the eCRF once per visit at Screening, Week 4, Week 8, Week 12, Week 16, Week 20, and Week 24. In addition, pre-dose and hourly cardiac monitoring (blood pressures and heart rates) for hours 1-6 will be recorded for all patients at the baseline visit and for the first 75 patients on Days 5 and 8.

Summary tables including actual values and change from baseline (defined as pre-dose on Day 1) values will be presented for vital signs including SBP (supine and standing), DBP (supine and standing), temperature, and HR by treatment group for the Safety population. On Day 1, hourly changes from pre-dose in blood pressures and heart rates will be shown for all patients. For all other visits starting at Week 4, only a single timepoint will be collected and shown.

For patients participating in cardiac monitoring on Days 5 and 8, a summary table will be provided that summarizes the hourly change from pre-dose assessment through hour 6 at each of the baseline, Day 5, and Day 8 visits by treatment group for heart rate and blood pressure.

Box plots will be provided to display the distribution of vital signs. In addition, line plots will be created to display the change from baseline over the entire study period and change from pre-dose in vital signs for the baseline, Day 5, and Day 8 visits.

The number and percentage of subjects with SBP  $> 180$  mmHG or  $< 90$  mmHG and HR  $< 40$  beats per minute will be summarized by visit for each treatment group. The number and percentage of subjects with clinically relevant abnormalities will be presented by treatment group. The criteria for clinically relevant abnormalities are shown in the following table. Vital signs will be presented by subject in listings.

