## 16.1.9 Documentation of Statistical Methods

Receptos, Inc.  
Protocol RPC01-201Statistical Analysis Plan – Part A, V1.2  
Date Issued: May 20, 2014**Table 10.3.1 Criteria to Determine Clinically Relevant Abnormalities in Vital Signs**

Vital Sign	Criteria for Abnormalities
Temperature	>38°C and an increase from pre-dosing of at least 1°C
Heart Rate	>120 beats per minute post-baseline, or an increase from pre-dosing of more than 20 beats per minute, or <45 beats per minute post-baseline, or a decrease from pre-dosing of more than 20 beats per minute
Systolic Blood Pressure	>180 mmHg post-baseline, or an increase from pre-dosing of more than 40 mmHg, or <90 mmHg post-baseline, or a decrease from pre-dosing of more than 30 mmHg
Diastolic Blood Pressure	>105 mmHg post-baseline, or an increase from pre-dosing of more than 30 mmHg, or <50 mmHg post-baseline, or a decrease from pre-dosing of more than 30 mmHg

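### The lowest-of-three predose baseline understates the within-arm mean supine fall after dosing, and protocol Sections 10.2.1.1 and 11.2.1 disagree on when that rule applies

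*Protocol*

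**What the plan says.** **Protocol Section 10.2.1.1** (first-dose monitoring). The supine predose measurement is "repeated 2 additional times to produce 3 readings for both heart rate and blood pressure (before the first dose of study drug only"). Only the lowest is kept: "The lowest predose value of supine heart rate and blood pressure (based on systolic blood pressure) will be recorded in the case report form". That value "will be recorded in the case report form and should be used for comparison to the postdose values". Vital signs are "measured before the first dose of study drug, then every hour for at least 6 hours thereafter", and no repeat readings are stated after dosing. Standing pressure is handled differently: "Orthostatic blood pressure will then be measured once with the patient in the standing position".

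**Protocol Section 11.2.1** (Vital Signs). Three measurements are taken at the Baseline visit and during titration (Days 5 and 8 as applicable), and "the lowest of the 3 measurements will be recorded on the eCRF, based on systolic BP". The text does not limit this to predose. At all other visits vital signs are assessed once.

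**SAP 10.3** (Part A). Baseline for vital signs is predose on Day 1, and changes from it are tabulated by visit. In addition, "On Day 1, hourly changes from pre-dose in blood pressures and heart rates will be shown for all patients". Table 10.3.1 includes change criteria such as "a decrease from pre-dosing of more than 20 beats per minute", alongside absolute limits. Neither document adjusts for the way the predose value is selected.

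**The concern.** The baseline is chosen because it is low, while each postdose value, under Section 10.2.1.1, is an unselected single reading. A patient whose heart rate and pressure did not change at all would on average show a rise. The tabulated within-arm mean change is therefore shifted toward no fall.

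This matters because heart-rate reduction after the first dose is a main safety question of the trial. Bradycardia is an adverse event of special interest, and the 7-day titration is there to attenuate the effect. SAP Section 10 tests no safety hypotheses, so readers will rely on the descriptive within-arm changes.

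There is also a conflict over how the values are obtained. Sites following Section 10.2.1.1 would compare a minimum with single readings, while sites following Section 11.2.1 might compare a minimum with minima. It is also unclear whether the systolic qualifier selects only the pressure, or the whole reading including its heart rate.

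**Working it through.** The documents give no figure to reproduce here, and no within-session SD.

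**Inputs from the documents**
- Three supine predose readings, lowest kept; single hourly postdose readings (protocol 10.2.1.1).
- Baseline is the Day 1 predose value (SAP 10.3).
- For scale only: Phase 1 titration, Day 1 change of -7.6 bpm on RPC1063 and -2.8 bpm on placebo (protocol 7.2.4).

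**Assumptions not in the documents**
- Independent normal readings around the patient's predose mean.
- Within-session SD *s* of 2 to 5 bpm for heart rate and 3 to 8 mmHg for systolic pressure.
- Within-session correlation ρ of 0 to 0.5 between heart rate and systolic pressure.

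**Step 1: expected minimum.** For three normal readings, E[min] = mean − 3*s*/(2√π) = mean − 0.846*s*. Numerical integration gives the same constant.

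**Step 2: bias in the mean change.** A single postdose reading is unbiased for the postdose level, so the mean fall is understated by 0.846*s*.

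| Quantity | SD | Understatement |
|---|---|---|
| Heart rate | 2 bpm | 1.7 bpm |
| Heart rate | 3 bpm | 2.5 bpm |
| Heart rate | 4 bpm | 3.4 bpm |
| Heart rate | 5 bpm | 4.2 bpm |
| Supine systolic | 3 mmHg | 2.5 mmHg |
| Supine systolic | 5 mmHg | 4.2 mmHg |
| Supine systolic | 8 mmHg | 6.8 mmHg |

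Against a true fall of 7.6 bpm, the heart-rate range is 1.69/7.6 = 22% to 4.23/7.6 = 56%. At *s* = 3, a true 7.6 bpm would be reported as 7.6 − 2.54 = 5.06 bpm.

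**Step 3: if heart rate is the value paired with the lowest systolic reading.** The bias becomes 0.846ρ*s*. It is 0 at ρ = 0. At ρ = 0.5 it is 0.85 bpm (*s* = 2) to 2.12 bpm (*s* = 5). The systolic bias stays at full size because selection is on systolic pressure itself.

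**Step 4: if Section 11.2.1 also covers the postdose Day 1 readings.** Both sides are then minima of three, the 0.846*s* terms subtract out when the SD is the same before and after dosing, and the bias in the Day 1 hourly mean change is 0. The Week 4 to Week 24 visits are assessed once and still use the Day 1 minimum as baseline, so supine systolic change at those visits stays biased under either section.

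**Step 5: between arms.** Every arm has the same rule. At *s* = 3, the reported mean falls are 7.6 − 2.54 = 5.06 and 2.8 − 2.54 = 0.26 bpm. Their difference is 4.80 bpm, the true value.

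**The case against.** **Scope.** Between-arm mean differences are unbiased. Standing pressure has one predose reading, so there is no selection. The absolute limits in SAP 10.3 and Table 10.3.1 (for example heart rate below 45 or 40 bpm, systolic below 90 mmHg) do not use the baseline. Every Part A patient has Day 1 Holter monitoring, analysed under its own plan and free of this rule. All of this stands and limits the point to within-arm supine change. Part B follows Section 10.2.1.1 but has no Holter monitoring, and its SAP is separate and not among the documents.

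**Conditionality.** The Day 1 hourly bias disappears if Section 11.2.1 governs postdose readings, and the heart-rate bias shrinks if heart rate is the paired value. This also stands. It makes reconciliation necessary, but it does not remove the later-visit systolic bias.

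**Clinical intent.** The lowest reading might be meant to offset predose arousal. Section 10.2.1.1 already requires 10 to 15 minutes of supine rest, and neither document gives this as a reason.

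**A stronger reading that is not supported.** A reader might infer that the rule also understates the true incidence of falls above 20 bpm. That does not follow. Noise in a single postdose reading inflates tail counts, while the low baseline deflates them. Suppose true falls are normal with mean 8 and SD 6 bpm (assumed). The true share above 20 is then P(Z > 2) = 2.3%. In simulation at one time point, with reading SD 2 to 5 bpm, the lowest-of-three baseline gives about 1.8% to 3.0%, which brackets the truth, and the mean-of-three baseline gives about 3.1% to 7.5%, which exceeds it. At a mean fall of 13 bpm the truth is 12.2%; lowest-of-three gives about 9% to 10% and mean-of-three 14% to 20%. No general direction is established, so no claim about incidence is made.

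**Conclusion.** The concern holds for within-arm mean supine change. If Section 10.2.1.1 is followed as written, the mean fall is understated by 0.846 within-session SD. For heart rate that is 1.7 to 4.2 bpm if the lowest heart rate is recorded, and 0 to about 2.1 bpm if it is the value paired with the lowest systolic reading. The supine systolic changes at Weeks 4 to 24 are biased whichever section governs Day 1. These sizes rest on the assumed SDs and correlation and on independent normal readings; the direction comes from the selection rule.

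The conflict between Sections 10.2.1.1 and 11.2.1 is a defect in itself, because the meaning of the hourly change depends on which section a site follows. It would be wrong to conclude that every change from predose is affected, or that the comparison with placebo is distorted in the mean.

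**What to change.** 1. Record all three predose supine readings on the eCRF.
2. In SAP 10.3 and Table 10.3.1, define the analysis baseline as the mean of the three, separately for heart rate, systolic and diastolic pressure. A mean of three and a single postdose reading are both unbiased for their own level, so the expected bias in mean change is 0. Carry the same definition into the separate Part B SAP.
3. Reconcile Sections 10.2.1.1 and 11.2.1 on when triplicates apply and on what the systolic qualifier selects, so that predose and postdose values follow the same rule, with no one-sided selection.

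The cost is two extra eCRF fields per parameter and short edits to the protocol and SAP. No extra measurement is needed, because the readings are already taken. Reported mean falls will become somewhat larger. The change is not offered as a correction to the threshold counts. The extended-monitoring criteria in Section 10.2.1.1 do not use the predose heart rate, and the clinical monitoring criteria are left unchanged.
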